5.2 RESPONSE CRITERIA

The primary efficacy endpoint for BTTC studies will be progression free survival (PFS) at six months from patient registration for bevacizumab naïve patients and at 3 months for patients with prior bevacizumab treatment. However, objective response status should be measured and recorded.

All measurements will be performed on the axial MRI T1 post contrast images when possible, although coronal images may be used if axial is not optimal for measurements (or CT post contrast if MRI is contraindicated). The same plane should be used for all measurements. Tumor size is defined as the largest (contrast enhancing) cross sectional area (largest cross-sectional diameter x largest diameter perpendicular to it).

- Evaluable for toxicity: All patients will be evaluated for toxicity from the time of their first treatment with Sorafenib or Everolimus.

- Evaluable for objective response: Only those patients who have measurable disease present at baseline, have received at least one cycle of therapy, and have had their disease re-evaluated will be considered evaluable for response. These patients will have their response classified according to the definitions stated below. (Note: Patients who exhibit objective disease progression prior to the end of cycle 1 will also be considered evaluable.)

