1.1.2 Phase II

1.1.2.1 Primary endpoints:

- 6 month progression free survival rate for glioblastoma patients with no prior bevacizumab exposure treated with everolimus and sorafenib at the maximum tolerated dose as determined in the phase I study.
- 3 month progression free survival rate for glioblastoma patients with prior bevacizumab exposure treated with everolimus and sorafenib at the maximum tolerated dose as determined in the phase I study.
- 6 month progression free survival rate for AG patients with no prior bevacizumab exposure treated with everolimus and sorafenib at the maximum tolerated dose as determined in the phase I study.

1.1.2.2 Secondary endpoints:

- Time to progression and overall survival for recurrent malignant glioma patients (Group A, Group B, and Group C) treated with everolimus and sorafenib measured from time of study enrollment.
- Objective response rate for recurrent malignant gliomas (Group A, Group B, and Group C) treated with everolimus and sorafenib
- Patient related outcome measures

To evaluate the occurrence of symptoms and correlate to disease progression and tolerance to treatment using the MD Anderson Symptom Inventory-Brain Tumor Module (MDASI-BT) self-reporting tool. This will include:

- To evaluate longitudinal changes in symptom measures and determine the impact of the therapy on these parameters.
- To measure symptom burden over the course of therapy to evaluate differences between patients individual symptom severity, overall mean symptom severity, and difference in scores on the interference items between responders and non-responders.
- To describe the variability of symptom severity longitudinally over the treatment course and follow-up period.

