5.2.1.3.5 Progression

- a. >25% increase in the sum of products of perpendicular diameters of enhancing lesions (over baseline if no decrease) on stable or increasing dose of corticosteroids.
and/or
- b. Significant increase in T2/FLAIR non-enhancing lesion on stable or increasing doses of corticosteroids compared to baseline scan or best response following initiation or therapy, not due to co-morbid events (radiation therapy, demyelination, ischemic injury, infection, seizures, postoperative changes, or other treatment effects).
- c. Any new lesion
- d. Clear clinical deterioration not attributable to other causes apart from the tumor (e.g., seizures, medication side effects, complications of therapy, cerebrovascular events, infection, etc.). The definition of clinical deterioration is left to the discretion of the treating physician, but it is recommended that a decrease in 20% of KPS or from any baseline to 50% or less be considered, unless attributable to comorbid events.
- e. Failure to return for evaluation due to death or deteriorating condition.

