5.2.1.3.6 Unknown

Progression has not been documented and one or more measurable or evaluable sites have not been assessed.

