5.2.7 Evaluability

Patients are required to receive at least 2 weeks of treatment of both agents, and the protocol defined evaluations are performed per protocol to be considered evaluable. Inevaluable patients will be replaced.

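### The objective response denominator leaves out patients who stop in cycle 1, or are not re-scanned, without progression, which very likely biases this secondary rate upward

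*Combined protocol and SAP*

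**What the plan says.** Section 1.1.2.2 lists as a secondary phase II endpoint: "Objective response rate for recurrent malignant gliomas (Group A, Group B, and Group C) treated with everolimus and sorafenib". Section 5.2 is the only place that says who enters the response calculation.

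- **Baseline condition:** "Evaluable for objective response: Only those patients who have measurable disease present at baseline".
- **Post-baseline conditions:** they must also "have received at least one cycle of therapy, and have had their disease re-evaluated will be considered evaluable for response".
- **Exception:** "Patients who exhibit objective disease progression prior to the end of cycle 1 will also be considered evaluable".

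Four other places bear on the point.

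- Section 5.2.1.3.5 lists clear clinical deterioration as progression under (d), and under (e) "Failure to return for evaluation due to death or deteriorating condition".
- Section 5.2.1.3.6 gives the status Unknown when "Progression has not been documented and one or more measurable or evaluable sites have not been assessed". Section 5.2.2 can carry this forward to an unknown best response.
- Section 5.2.7 has a separate rule: "Patients are required to receive at least 2 weeks of treatment of both agents", with the protocol evaluations done. Patients who fail it are replaced.
- Section 7.2 names no denominator for response and no all-treated response analysis. It does compare symptoms of responders and non-responders in the intent-to-treat population.

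**The concern.** Measurable disease at baseline is a proper condition for a response rate. It is fixed before treatment, and 5.2.1.3.2 does not allow a partial response without it. The other two conditions are met or missed after treatment starts. Failing them is often itself a poor outcome, such as intolerance or withdrawal. Both complete and partial response are judged on imaging, so a patient who is never re-scanned cannot be recorded as a responder. Leaving that patient out keeps the numerator and shrinks the denominator.

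What is at stake is how a reported response rate from small single-arm groups is read. Readers would take it as evidence of activity and compare it with rates elsewhere that may use all treated patients. The symptom comparison in 7.2 is affected too, because patients with unknown status are in the intent-to-treat population but belong to neither response class.

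**Working it through.** The plan states no response rate, response denominator or response-based sample size, so there is no figure of its own to reproduce on this point.

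**Step 1. Who is in the denominator?** Take patients with measurable baseline disease and read 5.2, 5.2.1.3.5 and 5.2.1.3.6 together.

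| Course in cycle 1 | Status | In the response denominator? |
|---|---|---|
| Completes the cycle, re-evaluated | As assessed | Yes |
| Radiographic progression | Progression | Yes, by the note |
| Dies, deteriorates, or does not return because of either | Progression under (d) or (e) | Probably; depends on *objective* |
| Stops for toxicity, no progression | Unknown if not re-scanned | No |
| Withdraws, no progression | Unknown if not re-scanned | No |
| Completes the cycle but is not re-scanned, no progression | Unknown | No |

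The last three rows are the clear exclusions. The first scheduled scan is at about the end of cycle 1 (3.6.1.2), so a patient who leaves before then will usually have none.

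**Step 2. Direction.** Let N be treated patients with measurable baseline disease, x the number dropped, d = x/N, R the responders among those kept, p the response rate among those kept, and q the response rate among those dropped.

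- Evaluable-only rate: p = R/(N − x).
- All-treated rate: (1 − d)p + dq.
- Difference: p − [(1 − d)p + dq] = d(p − q).

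The bias is upward whenever q is below p. With q = 0 the all-treated rate is R/N, and the ratio of the two rates is 1/(1 − d).

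**Step 3. Size.** The documents give neither d nor a response rate. Assume d from 5% to 30% and q = 0:

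- d = 5%: 1/0.95 = 1.05
- d = 30%: 1/0.70 = 1.43

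In whole patients, take N = 34, the Group A size. This assumes that all of Group A have measurable disease. Section 2.1.1.7 does not require that, so the real N may be smaller.

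| Dropped (nominal d) | 3 responders (3/34 = 8.8%) | 7 responders (7/34 = 20.6%) |
|---|---|---|
| 2 (5%) | 3/32 = 9.4% | 7/32 = 21.9% |
| 3 (10%) | 3/31 = 9.7% | 7/31 = 22.6% |
| 7 (20%) | 3/27 = 11.1% | 7/27 = 25.9% |
| 10 (30%) | 3/24 = 12.5% | 7/24 = 29.2% |

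With 7 responders the rise runs from 1.3 to 8.6 percentage points. It is zero if nobody is dropped, for example if everyone who leaves in cycle 1 has progression that counts.

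**Step 4. Does replacement remove it?** No. If x dropped patients are replaced, the treated total rises by x while R/(N − x) is still taken among those kept. With d redefined as the dropped share of all treated patients, the ratio is again 1/(1 − d).

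**Step 5. Primary designs.** The two-stage designs for Groups A and B in 7.2 count progression-free patients, not responses. Exact calculation gives alpha 4.7% and power 81.1% for Group A, and alpha 2.9% and power 80.1% for Group B. These agree with the stated 5% (as an upper bound) and 80%, and nothing in the response rule enters them.

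**The case against.** **Deaths and clinical failures are already handled.** A reader might infer that everyone who does not finish a cycle or is not re-scanned drops out, including those who die or deteriorate. The documents do not support that. The note keeps progressors in cycle 1. Section 5.2.1.3.5(d) and (e) make deterioration, and non-return because of death or deterioration, forms of progression, and they sit under the heading on objective status. The natural reading keeps these patients in. What remains is an ambiguity, because the note says *objective* and (d) and (e) need no scan.

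**The post-bevacizumab group.** A reader might also infer that the bias is worst in Group B, given survival of about 10 weeks after bevacizumab failure in section 1.2. That holds only if early deaths and deteriorations are excluded, which is the less likely reading. Group B is also scanned every 4 weeks for the first four scans. Nothing in the documents shows that stopping for toxicity or withdrawing without progression is more common there.

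**The direction is not certain.** Section 3.6.1.7 follows patients who leave therapy without progression until progression or new therapy. Someone who stopped in cycle 1 and was later found to have responded would fail the one-cycle condition, and dropping that patient would lower the rate. This stands, so the upward bias is very likely, not guaranteed.

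**Response matters little here.** It is secondary, with no target, test or stopping rule. The shift can be small beside sampling error: dropping 5 of 34 with 4 responders moves the rate from 11.8% (4/34) to 13.8% (4/29), while the exact 95% interval for 4/34 is 3.3% to 27.5%. This limits the importance of the point. It does not justify the rule, because a bias of likely direction is avoidable at almost no cost.

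**Conclusion.** The concern holds in a limited form. Section 5.2 conditions the response denominator on events after the start of treatment, and no all-treated rate is planned beside it. The patients clearly excluded are those with measurable disease who stop in cycle 1 for toxicity, withdraw, or are not re-scanned, in each case without documented progression. Whether death or deterioration before a scan is also excluded turns on one undefined word, and the better reading is that it is not.

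The rate is very likely biased upward by about 1/(1 − d). The range of 1.05 to 1.43 rests on an assumed d of 5% to 30% and on no responders among those dropped; the actual size cannot be found from the documents. No stated alpha, power or decision rule is affected. The text should be changed before response is reported, but the point does not threaten the primary analyses.

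Two inconsistencies add to the need. Section 5.2 asks for one cycle (28 days) and 5.2.7 for two weeks of both agents, so a patient treated for between two and four weeks can be judged differently under each. The symptom comparison in 7.2 needs a response class for patients whom 5.2 leaves unclassified.

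**What to change.** In section 5.2 or 7.2:

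1. Make the main response denominator all treated patients with measurable disease at baseline, for each of Groups A, B and C. Count missing or unknown status as non-response. A response documented after early stopping then still counts.
2. Report the evaluable-only rate as a supporting analysis, with the number excluded and the reasons.
3. State that progression under 5.2.1.3.5(d) or (e) counts as evaluable non-response, so that the note no longer depends on how *objective* is read.
4. Reconcile the evaluability rules in 5.2 and 5.2.7, and say which applies to which endpoint.

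This is a change of analysis text. It needs no new patients, visits or data, and no change to sample size. The response rate becomes slightly less favourable.

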5.2.1 Definitions of Response

5.2.1.1 Measurable Disease: Bi-dimensionally measurable CE lesions with clearly defined margins by CT or MRI scan, with a minimal diameter of 1 cm, and visible on 2 axial slices which are at least 5 mm apart with 0 mm skip. Measurement of tumor around a cyst or surgical cavity, if necessary, requires a minimum thickness of 3 mm.

5.2.1.2 Non-measurable Disease (contrast enhancing): Uni-dimensionally measurable lesions, masses with margins not clearly defined, lesions with maximal diameter < 1 cm.

5.2.1.3 Objective Status, To Be Recorded at Each Evaluation: If there are too many measurable lesions to measure at each evaluation, choose the largest two to be followed before a patient is entered on study. The remaining lesions will be considered evaluable for the purpose of objective status determination. Unless progression is observed, objective status can only be determined when ALL measurable and evaluable sites and lesions are assessed.

5.2.1.3.1 Complete Response (CR)

Complete disappearance of all CE measurable and evaluable disease. No new lesions. No evidence of non-evaluable disease. All measurable, evaluable and non-evaluable lesions and sites must be assessed using the same techniques as baseline. Patients must be on no steroids. There must be stable or improved non-enhancing (T2/FLAIR) lesions. Stable or improved clinically. Note: Patients with non-measurable disease cannot have a partial response. The best possible response is stable disease.

5.2.1.3.2 Partial Response (PR)

Greater than or equal to 50% decrease under baseline in the sum of products of perpendicular diameters of the two largest CE measurable lesions, sustained for at least 4 weeks. In the absence of a confirming scan 4 weeks later, this scan will be considered only stable disease. If more than two clearly defined lesions exist, the remaining lesions will be considered as evaluable. No progression of evaluable or non-measurable disease. No new lesions. All measurable and evaluable lesions and sites must be assessed using the same techniques as baseline. The steroid dose at the time of the scan evaluation should be no greater than the maximum dose used in the first 8 weeks from initiation of therapy. Stable or improved non-enhancing (T2/FLAIR) lesions on same or lower dose of corticosteroids compared to baseline. Stable or improved clinically. Note: Patients with non-measurable disease cannot have a partial response. The best response possible is stable disease.

5.2.1.3.3 Partial Response, Non-Measurable (PRNM)

Not applicable.

5.2.1.3.4 Stable/No Response

Does not qualify for CR, PR, or progression. The designation of stable disease requires a minimum of 4-week duration. All measurable and non-measurable sites must be assessed using the same techniques as baseline. Stable non-enhancing (T2/FLAIR) lesions on same or lower dose of steroids as compared to the baseline scan. In the event that the steroid dose has been increased, the last scan considered to show stable disease will be the scan obtained when the corticosteroid dose was equivalent to the baseline dose.

5.2.1.3.5 Progression

- a. >25% increase in the sum of products of perpendicular diameters of enhancing lesions (over baseline if no decrease) on stable or increasing dose of corticosteroids.
and/or
- b. Significant increase in T2/FLAIR non-enhancing lesion on stable or increasing doses of corticosteroids compared to baseline scan or best response following initiation or therapy, not due to co-morbid events (radiation therapy, demyelination, ischemic injury, infection, seizures, postoperative changes, or other treatment effects).
- c. Any new lesion
- d. Clear clinical deterioration not attributable to other causes apart from the tumor (e.g., seizures, medication side effects, complications of therapy, cerebrovascular events, infection, etc.). The definition of clinical deterioration is left to the discretion of the treating physician, but it is recommended that a decrease in 20% of KPS or from any baseline to 50% or less be considered, unless attributable to comorbid events.
- e. Failure to return for evaluation due to death or deteriorating condition.

5.2.1.3.6 Unknown

Progression has not been documented and one or more measurable or evaluable sites have not been assessed.

5.2.2 Best Response

This will be calculated from the sequence of objective statuses.

For patients with all disease sites assessed every evaluation period, the best response will be defined as the best objective status as measured according to Section **5.2.1**. If the response does not persist at the next regular scheduled MRI, the response will still be recorded based on the prior scan, but will be designated as a non-sustained response. If the response is sustained, e. g. still present on the subsequent MRI, it will be recorded as a sustained response, lasting until the time of tumor progression. Best response is unknown if the patient does not qualify for a best response or increasing disease and if all objective status determinations before progression are unknown.

5.2.3 Neurological Exam

Although not used for determining response, it is useful to evaluate improvement in the neurologic exam, (as compared to the baseline assessment), that should coincide with objective measurement of tumor size.

+2 Definitely better

+1	Possibly better
0	Unchanged
-1	Possibly worse
-2	Definitely worse

5.2.4 Performance Status:

Patients will be graded according to Karnofsky Performance Status (see Appendix **13.1**).

5.2.5 Time to Treatment Failure:

From date of registration to the date of first observation of progressive disease (as defined in Section **5.2.1**), non-reversible neurologic progression or permanently increased steroid requirement (applies to stable disease only), death due to any cause, or early discontinuation of treatment. If a patient is registered on the pre-operative portion of the study, the start date for calculation of time to event will be the date of first post-operative study drug administration.

5.2.6 Time to Death

From date of registration to date of death due to any cause.

5.2.7 Evaluability

Patients are required to receive at least 2 weeks of treatment of both agents, and the protocol defined evaluations are performed per protocol to be considered evaluable. Inevaluable patients will be replaced.

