1.2 BACKGROUND

Glioblastoma (GBM) is the most common primary brain tumor. With optimal treatment, consisting of focal radiotherapy with concurrent chemotherapy, followed by adjuvant chemotherapy, median survival is 14.6 months. (1) Cure is exceptional and most patients have

evidence of tumor progression within one year of diagnosis despite treatment. At progression, treatment options are limited and mostly ineffective; most clinical trials demonstrate six month progression free survival rate of only 9-15% and median overall survival is less than 25 weeks from time of tumor progression. (2) Recently, bevacizumab was approved for recurrent GBM based on data from Vredenburgh et al. and Kreisl et al.(3, 4) Data on patients who fail bevacizumab indicate a short survival, on the order of 10 weeks, an approximate PFS 3 and 6 months of 0%.

Anaplastic Astrocytoma (WHO grade III astrocytoma), although less aggressive than GBM, is a malignant tumor with a median survival of less than 3 years from diagnosis and estimated 5-year survival of 28% despite best treatment (2, 5)

Although malignant gliomas display genetic heterogeneity, several key proliferation and survival signaling pathways have been identified (6). Recent work has focused on targeting these tumor specific pathways in hopes of improving treatment efficacy and minimizing treatment toxicity. Because molecularly targeted agents have been mostly ineffective when used alone, combination therapy that inhibits multiple pathways is an appealing strategy.

1.2.1 Kinase Inhibitors:

Most growth factors initiate intracellular second messenger signaling systems through activation of tyrosine and/or serine/threonine kinase receptors. The kinase regions catalyze transfer of phosphate groups from adenosine triphosphate (ATP) to transmembrane receptors or signal transducers to initiate signaling pathway activation. The development of kinase inhibitors in cancer treatment has been stimulated by the success of imatinib mesylate in treating chronic myeloid leukemia (CML) and gastrointestinal stromal tumors (GIT). Imatinib mesylate specifically inhibits kinase activities associated with bcr-abl, c-kit, and PDGF receptor which are improperly regulated in CML and GIT.

Research has identified specific aberrant pathways that are thought to be important in malignant gliomas. (6) Specifically inhibiting these aberrant pathways may improve outcome without significant toxicity.

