2.3.4 Initiation of Therapy

Treatment may not be initiated until the participating institution receives a faxed or emailed copy of the patient's Registration Verification Letter from the Central Registration Office.

All Patients that are eligible to receive therapy must initiate treatment within 96 hours after the registration.

The BTTC Coordinating Center must be notified in writing of any exceptions to this policy.

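### Section 7.2 does not say whether early failures that Section 5.2.7 replaces stay in the PFS6 and PFS3 denominators

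*Combined protocol and SAP*

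**What the plan says.** - **Section 5.2.7 (Evaluability).** "Patients are required to receive at least 2 weeks of treatment of both agents, and the protocol defined evaluations are performed per protocol" for a patient to count as evaluable, and "Inevaluable patients will be replaced". The rule names no endpoint and lists no exceptions.
- **Section 5.2 (Response Criteria).** "The primary efficacy endpoint for BTTC studies will be progression free survival (PFS) at six months from patient registration" for bevacizumab-naïve patients, and at 3 months for those with prior bevacizumab. There is a carve-out, "Patients who exhibit objective disease progression prior to the end of cycle 1 will also be considered evaluable", but it sits under evaluability for objective response and covers objective progression only.
- **Section 5.2.1.3.5, item e.** Progression includes "Failure to return for evaluation due to death or deteriorating condition".
- **Section 2.4.** Phase II accrual is about 82 eligible patients. The sentence keeping patients removed for toxicity evaluable belongs to the Phase I paragraph.
- **Section 7.2.** Group A: 9 patients, then 34, promising if at least 9 are progression-free at 6 months. Group B: 14, then 32, promising if at least 2 are progression-free at 3 months. Patients are described as accrued and observed. Six-month PFS is also estimated by Kaplan-Meier. No PFS population is named and 5.2.7 is not mentioned. The only population named in Section 7 is intent to treat, for the symptom questionnaire.

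**The concern.** Take a patient who is registered, starts both drugs and dies on day 10. Under 5.2 and 5.2.1.3.5(e) that patient is a PFS failure. Under 5.2.7 the same patient is inevaluable and replaced. The second condition in 5.2.7 reaches further: the first scheduled scan comes at about 4 weeks (Section 3.6.1.2), so a patient who fails between week 2 and that scan could also be classed as inevaluable.

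The Simon rules use fixed denominators. If those denominators are filled with evaluable patients, people are removed because of a bad outcome and others take their places. The stage 1 decision is exposed too: with 9 patients and a threshold of 2, a single substitution can turn a stop into a continue. Because the analysis set is not fixed in advance, it could also be chosen once the counts are known, in a single-arm trial judged on whole-number cut-offs.

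**Working it through.** **1. Reproduce the plan's figures.** With n1 first-stage patients, continuation at g or more successes, total N and success at r or more:

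P(promising | p) = Σ over x from g to n1 of b(x; n1, p) × P(Bin(N − n1, p) ≥ r − x)

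Group A at p = 0.15 (n1 = 9, g = 2, N = 34, r = 9):

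| x | b(x; 9, 0.15) | P(Bin(25, 0.15) ≥ 9 − x) | product |
|---|---|---|---|
| 2 | 0.2597 | 0.0695 | 0.0181 |
| 3 | 0.1069 | 0.1615 | 0.0173 |
| 4 | 0.0283 | 0.3179 | 0.0090 |
| 5 | 0.0050 | 0.5289 | 0.0026 |
| 6 or more | | | 0.0005 |

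The sum is 0.0474, and power at 0.35 is 0.811. Group B (n1 = 14, g = 1, N = 32, r = 2) gives 0.0287 at 1% and 0.801 at 12%. Both designs meet the stated 5% and 80%. Group A has little slack below 5%.

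**2. Assumption.** Let q be the share of enrolled patients who are replaced. The documents give no figure. The ranges below run from half of the replaced being early failures (the other half succeeding at the overall rate) to all of them.

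**3. If 5.2.7 sets the denominators and the null is an all-patient rate p0.** The rate among counted patients is p0 × (1 − q/2)/(1 − q) if half are failures, and p0/(1 − q) if all are.

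| q | Group A rate, half / all | Group A type I error | Group B type I error |
|---|---|---|---|
| 0 | 15.0% | 4.7% | 2.9% |
| 1/35 = 2.9% (one replaced per 34 counted) | 15.2% / 15.4% | 5.1-5.5% | 3.0% |
| 5% | 15.4% / 15.8% | 5.4-6.2% | 3.0-3.2% |
| 10% | 15.8% / 16.7% | 6.3-8.2% | 3.2-3.5% |

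Group B reaches 5% only near q = 27% with all replaced being failures. As a stress case, read Section 1.2's survival of about 10 weeks after bevacizumab failure as an exponential median (an assumption). Deaths before a 4-week scan are then 1 − 2^(−4/10) = 24.2%, and Group B's error is 4.7%.

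**4. How far this depends on the true rate.** Section 1.2 says "most clinical trials demonstrate six month progression free survival rate of only 9-15" per cent, so the 15% null is the top of the quoted range. At a true 12%, Group A's error is 1.3% at q = 0 and reaches 5% only near q = 21%, even if all replaced are failures.

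**5. If 15% is an evaluable-patient rate.** Using 5.2.7 then causes no inflation. Counting everyone lowers the rate to p0 × (1 − q)/(1 − q/2) (half) or p0 × (1 − q) (all). Group A's error becomes 4.1-3.6% at q = 5% and 3.5-2.6% at q = 10%.

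**6. Effect on the estimate.** At the Group A boundary, 9/34 = 26.5%. With one replaced failure counted it is 9/35 = 25.7%, and with four it is 9/38 = 23.7%. The exact 95% interval for 9/34 is 12.9-44.4%. At the Group B boundary, 2/32 = 6.3% becomes 2/36 = 5.6% with four.

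**The case against.** Replacing a patient is an accrual rule. It does not by itself take that patient out of the PFS analysis, and nothing in the documents says it does. A statistician could replace the day-10 death and still count it as a failure. The remaining wording favours that reading: PFS starts at registration, early death is progression, accrual is set in eligible patients, and 7.2 speaks of patients accrued and observed. Section 5.2.7 also sits within the response criteria. This stands. A reader might infer that the plan removes early failures from its primary endpoint, or that 5.2 and 5.2.7 cannot both be followed. The documents support neither.

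What the objection does not do is settle the denominator. The two-week rule differs from the one-cycle rule for objective response, so it is not a restatement of that rule. If everyone accrued is counted, 7.2 would still need to say how replacements fit with a fixed 34 and 32.

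It is also fair that the error-rate effect needs three conditions at once: evaluable denominators, a null meant for all patients, and a true rate at the null. That limits the weight of the point.

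**Conclusion.** The point holds as an unspecified primary analysis set. It is worth fixing, at the lower end of that category. If 5.2.7 governs, PFS6 and PFS3 are biased upward as estimates for all registered patients; against an evaluable-patient target they are not.

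A reader might infer that Group A's 5% error rate is broken. That follows only if the true all-patient rate is exactly 15%, and then by a modest amount (5.1-5.5% with one replaced per 34 counted, 6.3-8.2% at an assumed q of 10%). At a true 12%, or with an evaluable-patient null, it does not follow at small q. No breach is shown for Group B at the values examined, so the concern there is the PFS3 estimate. In both groups the shift at the decision boundary is small, and in Group A it is well inside the confidence interval. All of this rests on q, which the documents do not give.

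**What to change.** In Section 7.2, state that:

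- the primary PFS6 and PFS3 counts, at both Simon stages, and the Kaplan-Meier estimates include all eligible registered Phase II patients. An acceptable alternative is all eligible patients who start treatment, with any registered but untreated patients reported; these should be few, since "All Patients that are eligible to receive therapy must initiate treatment within 96 hours after the registration";
- progression, death or clinical deterioration at any time before a patient meets 5.2.7, whether before 2 weeks or before the first scheduled evaluation, is a failure and is not replaced;
- 5.2.7 does not define the PFS denominator.

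Keep the 5.2.7 evaluable set as a sensitivity analysis, and define what two weeks of both agents means when sorafenib is scheduled 7 days on and 7 days off. Group A is closed, so apply the rule to its analysis set and report the number of replacements and the reasons. Group B is not marked closed in Section 2.4 and can be handled prospectively.

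**Cost.** A few sentences and a replacement count, with no extra patients. Observed rates become slightly less favourable. If the 35% and 12% targets were meant for evaluable patients, power with everyone counted falls as follows (half to all of the replaced being failures):

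| | q = 0 | q = 5% | q = 10% |
|---|---|---|---|
| Group A | 81.1% | 78.6-76.1% | 75.8-70.1% |
| Group B | 80.1% | 79.0-77.9% | 77.8-75.4% |
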